## 9 STATISTICAL CONSIDERATIONS

### 9.1 Statistical Hypotheses

- Primary Objective:

**Aim 1. Characterize the relationship between baseline sleep deficiency and self-management processes.** H1. Greater baseline sleep deficiency (shorter sleep duration, poorer sleep quality, increased insomnia symptoms, greater wake time after sleep onset) will be associated with lower activation, lower pain self-efficacy, and lower use of self-management skills from pre- to post-treatment. H2. Positive and negative affect and executive functioning will mediate the relationship between sleep deficiency and self-management processes.

- Secondary Objective:

**Aim 2. Determine the effect of baseline sleep deficiency on treatment acceptability, engagement, and benefit from an internet-delivered pain self-management intervention.** H3. Greater sleep deficiency will be associated with lower perceptions of treatment acceptability and engagement (fewer logins, fewer completed treatment modules and assignments). H4. Greater sleep deficiency will be associated with less benefit (fewer improvements) in ratings of global health, fatigue, pain symptoms, and pain-related disability following pain self-management intervention. H5. Positive and negative affect and executive functioning will mediate the relationship between sleep deficiency and treatment acceptability, engagement and benefit.

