### 9.2 Sample Size Determination

Aim 1: A series of Monte Carlo simulations were conducted to evaluate longitudinal mediation (70). Results indicate 80% power for a sample size of 75 given a mediated effect of approximately 27% or larger and specific indirect effects of  $R^2 = .12$  or larger.

Aim 2: A series of Monte Carlo simulations were specified (27) to evaluate power to detect variance in linear change. Results indicate a sample size of 52 is needed. Adding predictive structural paths to the simulated LGMs indicated that a sample size of  $N = 75$  would be powered at .80 to detect an effect size as small as  $R^2 = .06$  and .03 for the slope and intercept, respectively (71).

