### 9.3 Statistical Analyses

Data will be reviewed for completeness and errors including consistency checks for relevant variables. Tabular and graphical methods of data exploration including frequency tables, scatterplots, and box plots will be used to explore distributions of study variables. For the primary analytic plan, we will rely

on panel and latent growth models (LGM), within the structural equation modeling (SEM) framework (55-57). Both approaches can be implemented within a manifest and/or latent variable context (58). Unlike traditional repeated-measures analysis of variance, SEM allows for a more accurate and flexible approach to analyzing repeated measures data by simultaneously modeling change in the means (fixed effects) and in the variance and covariance of initial level and change (random effects) (56, 59-61). We include biological covariates of age, sex, and pain location in all models. We expect 10% attrition for a final projected sample size of  $n = 72$ . Full Information Maximum Likelihood (FIML) estimation will be used to handle missing data related to attrition and non-response (62) incorporating robust standard errors or bootstrapping to correct for non-normality (61). FIML estimation improves accuracy and power relative to other missing data handling methods (63, 64).

**Aim 1. Characterize the relationship between baseline sleep deficiency and self-management processes.** We will use structural equations (65, 66) to assess interrelations, direct effects, and indirect mediation effects in a longitudinal panel model. Mediation will be tested by decomposing a total effect of each sleep deficiency measure (duration, wake time, quality, insomnia symptoms) on self-management processes into direct effects and indirect effects (65, 66). Significance tests of indirect effects will be carried out using the Monte Carlo (*empirical-M*) method to obtain 90% asymmetric confidence intervals (67-69).

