Expected Results, Interpretation, and Possible Pitfalls. We expect the higher the level of sleep deficiency the higher negative affect, lower positive affect, *lower executive functioning*, lower the behavioral activation, self-efficacy, and self-regulation at baseline. There will likely be an indirect effect of sleep deficiency on affect *and executive function* and of affect *and executive function* on self-management processes. *We also expect that a significant indirect effect will indicate that sleep deficiency affects change in self-management processes by influencing affect or executive function.*

**Aim 2. Determine the effect of baseline sleep deficiency on treatment acceptability, engagement with, and benefit from an internet-delivered pain self-management intervention.** We will use LGMs to model individual differences in final acceptability and engagement status and the rates of change in global health, pain symptoms, fatigue, and pain-related disability (56, 59-61) and to test the proposed predictive and mediated effects.

Expected Results, Interpretation, and Possible Pitfalls. We expect that global health will improve over the course of the study while pain, fatigue, and pain-related disability will decrease. We also expect that participants will significantly vary around the average intercept and slope. We expect the higher the initial level of sleep deficiency the shallower the increase in global health over time and the shallower the decline in pain, fatigue, and pain-related disability. Across all models we expect less than 10% attrition over the course of the study based on our prior work (27). We will use the maximum likelihood estimation option in the Mplus 7.3 software program to deal with missing data and use the robust standard error option to correct for non-normality (61).

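### Aim 2 power of .80 at N = 75 (section 9.2) cannot be reproduced from the reported inputs, and the intercept figure (R² = .03) is not credible as the power of a separate single-path test

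*Combined protocol and SAP*

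**What the plan says.** Section 9.2 bases the Aim 2 sample size on Monte Carlo simulation of latent growth models. With predictive paths added, N = 75 "would be powered at .80 to detect an effect size as small as" R² = .06 for the slope and .03 for the intercept, the two values being assigned to the two factors respectively. For Aim 2 it states no alpha, sidedness, predictors, population variances or reliability, and it does not say whether R² is total or incremental.

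Section 9.3 bears on this in three ways:
- Covariates: "We include biological covariates of age, sex, and pain location in all models". The variance they are expected to explain is not given.
- Use of the models: they will "model individual differences in final acceptability and engagement status and the rates of change in global health", pain, fatigue and disability, and serve "to test the proposed predictive and mediated effects".
- Analysed N: "We expect 10% attrition for a final projected sample size of" 72, and later "Across all models we expect less than 10% attrition over the course of the study". Missing data are handled by full information maximum likelihood (FIML).

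Section 9.1 makes Aim 2 the secondary objective. H3 reads "Greater sleep deficiency will be associated with lower perceptions of treatment acceptability and engagement". H4 reads "Greater sleep deficiency will be associated with less benefit (fewer improvements", which is a statement about change. The only significance convention in the plan is the 90% interval for the Aim 1 indirect effects.

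**The concern.** An R² of .03 or .06 is small for about 75 participants, and .80 power for a single path of that size looks too high. The R² that can be detected depends on alpha, on what else is in the model and on how well the growth factors are measured, and none of these is reported.

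Null Aim 2 results will be read against the .80 claim. H4 concerns change, so the slope figure bears on it directly. Section 9.2 does not say which hypothesis the intercept figure serves. If it is meant to cover the final acceptability and engagement status named in section 9.3 (H3), and power at R² = .03 is nearer a third or a half, a null H3 would say little about effects of that size.

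**Working it through.** **Inputs from the plan.** N = 75, power .80, R² = .06 (slope) and .03 (intercept), from section 9.2. Enrolment is 80, and 10% attrition gives 80 × 0.9 = 72 (section 9.3).

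**Assumptions.** Two-sided alpha of .05 or .10. The .10 column also approximates one-sided .05, since H3 and H4 are directional.

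**1. Attempt to reproduce the stated .80.** One predictor, total R², growth factors observed without error, no missing data. Noncentral F test with 1 and N − 2 df and λ = N·R²/(1 − R²).
- Slope: λ = 75 × .06/.94 = 4.79.
- Intercept: λ = 75 × .03/.97 = 2.32.
- Required for .80 power: λ of about 8.1 at .05, or 6.3 at .10.

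| N | Slope / intercept, .05 | Slope / intercept, .10 |
|---|---|---|
| 72 | 56% / 31% | 68% / 43% |
| 75 | 58% / 32% | 70% / 45% |
| 80 | 61% / 34% | 72% / 47% |

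Two-sided .20 at N = 75 gives 81.5% and 59.5%. To reach .80 at N = 75, alpha would have to be about .18 for the slope and .47 for the intercept. Large-sample Wald, Fisher z and R²-read-as-f² variants also fall short at .05 and .10: 55% to 59% and 68% to 71% for the slope, 32% to 33% and 44% to 45% for the intercept.

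In this one-predictor case the smallest R² with .80 power at N = 75 is .097 (.05) or .077 (.10). Measurement error would raise it.

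**2. R² as an increment over other predictors.** If the others explain a share Rc, then λ = N·R²/(1 − Rc − R²), with N − 6 denominator df. The 4 covariate terms are an assumption: age, sex, and pain location in three categories. Solving for the Rc that gives .80 at N = 75:

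| | .05 | .10 |
|---|---|---|
| Slope, R² = .06 | 38% | 23% |
| Intercept, R² = .03 | 69% | 61% |

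Check at .05: slope 75 × .06/(1 − .383 − .06) = 8.1; intercept 75 × .03/(1 − .691 − .03) = 8.1.

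With all 80 complete, the slope needs 34% or 18% and the intercept 67% or 59%. As multiple correlations at N = 75, the slope needs about .62 or .48 and the intercept about .83 or .78.

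Power at N = 75 for a given Rc, slope / intercept:
- Rc = 20%: 68% / 39% (.05), 79% / 52% (.10).
- Rc = 40%: 81% / 50% (.05), 89% / 63% (.10).

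**3. Joint 2-df test of both paths.** λ = N·b′S⁻¹b, where b holds the two paths (√.03, √.06) and S is the residual covariance matrix of the two factors.
- Uncorrelated residuals: λ = 75 × (.03/.97 + .06/.94) = 7.11, giving about 64% (.05) or 76% (.10).
- Assumed residual correlation of −.3 with same-signed paths: λ = 10.0, giving about 80% or 88%.

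**The case against.** The strongest reply is that a simulation of the planned model outranks a closed-form benchmark. The planned model has covariates and mediators, and a predictor that removes residual variance raises power for the path of interest. This stands for the slope: other predictors explaining 23% to 38% of slope variance would deliver the stated figure, and an intercept–slope correlation of about .48 to .62 would be enough by itself. It does not extend to the intercept. Age, sex and pain location are the only covariates named for all models, and nothing in the documents suggests that they, with or without the mediators, explain 61% to 69% of intercept variance.

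A second reply is that one power figure for a pair of R² values may describe a joint test. A negative residual correlation is plausible, because section 5.1 requires a minimum pain and interference score at entry. A joint test could then give about .80 at two-sided .05. This limits the criticism of the intercept to separate single-path tests. It does not support the claim as written: section 9.2 assigns an R² to each factor, describes no joint test, and gives no residual correlation.

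Third, the simulation itself is not shown. A reader might infer that it contains an error, or that the slope claim is optimistic. The documents support neither inference: no calculation in them is shown to be wrong, and plausible but unstated settings would yield the slope figure.

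**Conclusion.** The point holds in a limited form. As reported, .80 at N = 75 does not follow for either factor: separate single-path tests fall short by about 22 points (slope) and 48 points (intercept) at two-sided .05, and by 10 and 35 points at two-sided .10. The slope figure is not reproducible from the reported inputs. The intercept figure is not credible as a separate single-path power. Both statements rest on the assumed alphas, and the percentages also on one predictor, total R² and no measurement error.

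Three further inferences should be resisted:
- The values for 80 complete cases (61%/34% at .05) are not ceilings on the planned model, and R² of about .09 to .10 (.05) or .07 to .08 (.10) for N = 72 to 80 is not a general threshold. Both hold only for a single predictor without covariates. With 40% explained elsewhere, the smallest detectable increment at N = 75 falls to .058 (.05) or .047 (.10).
- It is not established that H3 has 32% to 47% power, because section 9.2 does not tie the intercept figure to H3.
- The gap between 75 in section 9.2 and 72 in section 9.3 does not explain the shortfall. It costs about 2 points (57.9% against 56.1% for the slope at .05), and FIML retains partial data.

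Aim 2 is secondary and the remedy is cheap. This should be fixed, with medium confidence because the simulation cannot be seen.

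**What to change.** Keep enrolment at 80. Rerun the Aim 2 simulation for 80 enrolled with about 10% attrition under FIML, and use the same analysed N in sections 9.2 and 9.3. Report with it:
- alpha and sidedness;
- predictors and covariates, with the variance they are assumed to explain;
- whether R² is total or incremental;
- the assessment waves and the assumed reliability;
- whether the slope and intercept paths are tested separately or jointly, with the residual correlation if jointly;
- which hypothesis each figure serves.

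Unless the rerun supports .80 at R² = .06 and .03, replace the claim with the detectable R² that it gives, and describe smaller effects as estimated with an interval rather than as powered. Do not use the one-predictor benchmark as a pass/fail check on the covariate-adjusted model.

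The cost is one simulation rerun, a record of its inputs and some rewording. Enrolment, analysis and conduct do not change. The stated detectable effects may become less favourable, most likely for the intercept. If the existing simulation is sound, documenting its inputs would settle the matter.

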### 9.3 Statistical Analyses

Data will be reviewed for completeness and errors including consistency checks for relevant variables. Tabular and graphical methods of data exploration including frequency tables, scatterplots, and box plots will be used to explore distributions of study variables. For the primary analytic plan, we will rely

on panel and latent growth models (LGM), within the structural equation modeling (SEM) framework (55-57). Both approaches can be implemented within a manifest and/or latent variable context (58). Unlike traditional repeated-measures analysis of variance, SEM allows for a more accurate and flexible approach to analyzing repeated measures data by simultaneously modeling change in the means (fixed effects) and in the variance and covariance of initial level and change (random effects) (56, 59-61). We include biological covariates of age, sex, and pain location in all models. We expect 10% attrition for a final projected sample size of  $n = 72$ . Full Information Maximum Likelihood (FIML) estimation will be used to handle missing data related to attrition and non-response (62) incorporating robust standard errors or bootstrapping to correct for non-normality (61). FIML estimation improves accuracy and power relative to other missing data handling methods (63, 64).

**Aim 1. Characterize the relationship between baseline sleep deficiency and self-management processes.** We will use structural equations (65, 66) to assess interrelations, direct effects, and indirect mediation effects in a longitudinal panel model. Mediation will be tested by decomposing a total effect of each sleep deficiency measure (duration, wake time, quality, insomnia symptoms) on self-management processes into direct effects and indirect effects (65, 66). Significance tests of indirect effects will be carried out using the Monte Carlo (*empirical-M*) method to obtain 90% asymmetric confidence intervals (67-69).

Expected Results, Interpretation, and Possible Pitfalls. We expect the higher the level of sleep deficiency the higher negative affect, lower positive affect, *lower executive functioning*, lower the behavioral activation, self-efficacy, and self-regulation at baseline. There will likely be an indirect effect of sleep deficiency on affect *and executive function* and of affect *and executive function* on self-management processes. *We also expect that a significant indirect effect will indicate that sleep deficiency affects change in self-management processes by influencing affect or executive function.*

**Aim 2. Determine the effect of baseline sleep deficiency on treatment acceptability, engagement with, and benefit from an internet-delivered pain self-management intervention.** We will use LGMs to model individual differences in final acceptability and engagement status and the rates of change in global health, pain symptoms, fatigue, and pain-related disability (56, 59-61) and to test the proposed predictive and mediated effects.

Expected Results, Interpretation, and Possible Pitfalls. We expect that global health will improve over the course of the study while pain, fatigue, and pain-related disability will decrease. We also expect that participants will significantly vary around the average intercept and slope. We expect the higher the initial level of sleep deficiency the shallower the increase in global health over time and the shallower the decline in pain, fatigue, and pain-related disability. Across all models we expect less than 10% attrition over the course of the study based on our prior work (27). We will use the maximum likelihood estimation option in the Mplus 7.3 software program to deal with missing data and use the robust standard error option to correct for non-normality (61).

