## 1.2 Schema

### *Study Flow*

## 1.3 Schedule of Activities

	Pre-Screening	Consent	Time 1	Time 2	Time 3	Time 4
EMR Review	X					
Eligibility						
Informed Consent		X				
Demographics			X			
Sleep assessment			X		X	X
Outcome evaluation			X		X	X
Mediator evaluation				X		
Intervention			X	X		
Adverse events reporting				X	X	X

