## 8 STUDY ASSESSMENTS AND PROCEDURES

### 8 STUDY ASSESSMENTS AND PROCEDURES/EVALUATIONS

#### 8.1 Study Procedures/Evaluations

Assessments will occur at baseline ( $T_1$ ), immediately after intervention (2 months;  $T_2$ ), and repeated at 6 months ( $T_3$ ). Mediators will be assessed at an additional mid-treatment (4 weeks) data point. The intervention phase will last 2 months (8 weeks). All questionnaires will be administered using Research Electronic Data Capture (REDCap), a secure web-based tracking and on-line data acquisition system (40). We have used this system successfully in multiple studies to date. Estimated time burden is 10 minutes for parents and 40 minutes for teens. Response burden is minimized by the online administration, which allows saving and storing of responses.

**Screening Measures.** Participants will complete the Pediatric Sleep Questionnaire (41) to screen for sleep-disordered breathing. If they screen positive they will be referred for clinical evaluation and will not be enrolled. Parents will complete a Demographic Questionnaire to assess sociodemographic variables and pain history.

**Mediators.** Positive and negative affect will be assessed with the Positive and Negative Affect Scale-Child version (PANAS-C; (48). The PANAS-C consists of two mood scales with 10-items each rated on a 5-point scale for assessing positive (e.g., inspired, strong) and negative affect (e.g., guilty, scared). Both scales are internally consistent, uncorrelated, and stable over a 2-month time period; good convergent and discriminant validity have also been demonstrated (48). Executive functioning will be assessed with the Behavior Rating Inventory of Executive Function (BRIEF-2) (49), a short 12-item well validated self-report measure that assesses executive function behaviors (e.g., inhibitory control, working memory, planning and organization) in home and school environments providing three indices of regulation, Behavioral, Emotional, and Cognitive.

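### Section 9.3 does not say that the week-4 mediators are adjusted for their own baseline, and the documents disagree on whether that baseline is collected, so a sleep–mood link that predates treatment could be read as mediation

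*Combined protocol and SAP*

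**What the plan says.** All references are to the combined protocol and SAP.

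- **Hypotheses (Section 9.1).** H2, under the primary objective, and H5, under the secondary, make affect and executive function mediators of the effect of sleep deficiency.
- **Models (Section 9.3).** The covariate rule is "We include biological covariates of age, sex, and pain location in all models". Aim 1 uses structural equations "to assess interrelations, direct effects, and indirect mediation effects in a longitudinal panel model". The mediator waves, lags and autoregressive paths are not written out. Aim 2 uses latent growth models (LGMs), also for mediation, without saying how the mediator enters. Under Aim 1, indirect effects are tested with 90% asymmetric Monte Carlo intervals.
- **Mediator timing.** Section 8.1 lists baseline, 2 months and 6 months, and then: "Mediators will be assessed at an additional mid-treatment (4 weeks) data point". In Section 1.3 the row "Mediator evaluation" has one mark, under Time 2. The sleep and outcome rows are marked at Times 1, 3 and 4.
- **Expected baseline association (Section 9.3).** Greater sleep deficiency is expected to go with worse affect and executive function, in a sentence that ends "lower the behavioral activation, self-efficacy, and self-regulation at baseline".
- **Stability (Section 8.1, PANAS-C only).** "Both scales are internally consistent, uncorrelated, and stable over a 2-month time period".
- **Planned interpretation (Section 9.3).** "a significant indirect effect will indicate that sleep deficiency affects change in self-management processes by influencing affect or executive function".

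**The concern.** The first leg of the mediation has the week-4 mediator as its outcome and baseline sleep as its predictor. Suppose sleep and mood are already associated at baseline, as the plan expects, and mood carries over from baseline to week 4. Baseline sleep will then predict week-4 mood even if sleep has no further effect on it. Age, sex and pain location do not remove this. Nor does adjusting the outcome for baseline self-management, because the problem lies in the sleep-to-mediator leg.

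The stakes are considerable because mechanism is the purpose of this single-arm study, H2 belongs to the primary objective, and Section 9.3 fixes in advance a mechanistic reading of a significant indirect effect. If no T1 mediator score is collected, the alternative explanation cannot be examined at all.

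**Working it through.** **1. The plan's own figures.** The final sample follows from 10% attrition: 80 × (1 − 0.10) = 72. Section 9.2 states 80% power for Aim 1 mediation at N = 75 with R² = .12. This cannot be firmly reproduced, because the alpha level and path values are not given. On one reading, both paths have R² = .12, so λ = 75 × 0.12/0.88 = 10.2. Power per path is then 0.884 at two-sided 5% and 0.936 at 10%. Joint power is 0.884² = 0.78 and 0.936² = 0.88. Neither figure shows whether the baseline mediator was in the model.

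**2. Is there a baseline mediator score?** Section 1.3 shows none under Time 1. Section 8.1 calls week 4 an additional point, and Section 9.3 predicts associations at baseline. Both of these imply a T1 score. The documents conflict. Section 8.1 also labels the post-treatment visit T2, but the schedule has no mediator mark under Time 1 whichever numbering is used.

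**3. What the unadjusted path estimates.** With standardized variables, let r be the correlation of sleep with the baseline mediator, s the mediator's baseline-to-week-4 path, a the effect of sleep on the week-4 mediator given its baseline, and b the mediator-to-outcome path.

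- Without the baseline mediator: indirect effect = (a + r·s)·b
- With it: indirect effect = a·b

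With a = 0 and b = 0.35, the unadjusted value is 0.2 × 0.5 × 0.35 = 0.035 in the mildest setting below and 0.4 × 0.7 × 0.35 = 0.098 in the strongest. Simulated means were 0.034 and 0.096 unadjusted, and −0.002 and −0.001 adjusted.

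**4. How often the 90% interval excludes zero when a = 0.** The values of r, s and b are assumptions; the documents give none. Both simulations use n = 72, b = 0.35, a Monte Carlo interval, and the baseline outcome in the outcome model. Simulation A (2,000 trials per setting, four covariates) generates baseline sleep from mood. Simulation B (1,000 trials, three covariates) generates baseline mood from sleep.

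| r | s | A: unadjusted | A: adjusted | B: unadjusted | B: adjusted |
|---|---|---|---|---|---|
| 0.2 | 0.5 | 19.2% | 8.2% | 19.3% | 8.5% |
| 0.2 | 0.7 | 32.0% | 7.5% | 30.7% | 6.9% |
| 0.3 | 0.5 | 33.8% | 9.0% | 31.2% | 6.8% |
| 0.3 | 0.7 | 54.2% | 7.4% | 52.5% | 6.6% |
| 0.4 | 0.5 | 45.4% | 8.8% | 47.5% | 8.9% |
| 0.4 | 0.7 | 72.9% | 6.6% | 71.6% | 6.2% |

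The nominal rate is 10%. Extending B to r = 0.5 and b = 0.5 widens the ranges to 19%–93% unadjusted and 6%–12% adjusted. A and B agree within 3 points although they reverse the direction of the baseline association, so the data cannot reveal that direction.

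**5. Power with a true a of 0.25 SD (Simulation A).**

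- r = 0: 64.1% unadjusted and 70.8% adjusted at s = 0.5; 62.6% and 70.4% at s = 0.7.
- r = 0.2 to 0.3: 86.8%–93.8% unadjusted and 64.4%–70.4% adjusted. The unadjusted figure includes the r·s·b component.

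**The case against.** **Silence is not omission.** A reader might infer that the plan leaves the baseline mediator out of every model. The text does not show that. The covariate sentence covers biological covariates and is not a full list of model terms; sleep itself is absent from it. A longitudinal panel model often carries autoregressive paths. This stands: the plan is silent. The defence reaches Aim 1 only, since the LGMs for H5 give no comparable hint.

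**The baseline score may not exist.** A reader might also take it as settled that the mediators are scored at baseline. Given Section 1.3, it is not.

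**The unadjusted rejections are not errors in every sense.** The background in Section 2.2 has short sleep worsening affect. If the baseline association arose that way, baseline mood lies on the causal path. The unadjusted analysis would then detect a real effect that predates treatment, and the adjusted one would remove it. H2 does not restrict mediation to change in the mediator after baseline, and in the interpretive sentence the word change attaches to self-management. This stands, so 19% to 73% cannot be called the trial's false-positive rate. It is a reason to report both fits. It does not make the unadjusted fit able to show that sleep influences the mediator, because mood disturbing sleep or a shared cause would give the same result.

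**The size is uncertain.** No document value narrows the range. The stability statement covers PANAS-C, not BRIEF-2, and gives no coefficient; at s = 0.5 the two scores share only 0.5² = 25% of variance. The LGM mediation for H5 was not simulated, and acceptability and engagement have no pre-treatment score, so the figures apply to Aim 1-type models.

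**Power is not a main argument for adjusting.** The gain of 6 to 8 points needs sleep unrelated to baseline affect, which is contrary to what Section 9.3 expects.

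**Conclusion.** The concern holds in a limited form. Section 9.3 does not state that the week-4 mediator is adjusted for its baseline in H2 or H5, and Sections 1.3, 8.1 and 9.3 conflict on whether that baseline is collected. Without the adjustment, the sleep–mood association that the plan itself expects at baseline can by itself yield a significant indirect effect.

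At the mildest assumed setting the rejection rate is almost twice the nominal 10%; across the assumed range it is about 19% to 73%, against 7% to 9% with adjustment. These rates measure error only for the claim that sleep changes the mediator during treatment. They rest on the assumed r, s and b, and on a model of the Aim 1 type. The documents do not support the stronger conclusions that the sponsor has decided against adjustment or that the mediation result would be false. They do support saying that, as written, the plan cannot carry its own mechanistic reading.

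**What to change.** 1. Reconcile Section 1.3 with Section 8.1 so that PANAS-C and BRIEF-2 are collected at T1, and use one numbering of time points.
2. In Section 9.3, for H2 and H5, name the mediator wave and enter the T1 mediator score in both the week-4 mediator equation and the outcome equation. For Aim 1 this means writing out the autoregressive path; for Aim 2, state how the mediator and its baseline enter the LGMs.
3. Rest the interpretive sentence in Section 9.3 on that model. Report the fit without the baseline mediator as a secondary description of the total association.
4. If T1 scores turn out not to exist, describe the indirect effect as an association and withdraw the mechanistic reading.

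The cost is SAP wording and one covariate per mediator in each of the two equations, provided that T1 scores are collected; otherwise it adds two short questionnaires at baseline. The adjusted estimate covers only the treatment-period path and is usually smaller. Its power is about 64% to 70% at an assumed effect of 0.25 SD when sleep and baseline affect are correlated at 0.2 to 0.3. That is below the 80% in Section 9.2, although the two figures rest on different effect assumptions. The plan should say so.
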